**Table 3 Blinding of study epoch**

Study Epoch	Blinding
Epoch 001	open

- Sampling schedule: Blood samples will be drawn from all subjects at the following time points:
  - Pre-Bst: Before the booster dose administration, a volume of approximately 5 mL of whole blood (to provide approximately 1.7 mL of serum) will be collected.
  - Post-Bst: One month after the booster dose, approximately 5 mL of whole blood (to provide approximately 1.7 mL of serum) will be collected.
- Type of study: extension of other protocol(s) 116945 [DTPA (BOOSTRIX)-047] and 201330 [DTPA (BOOSTRIX)-048 PRI].
- Data collection: Electronic Case Report Form (eCRF).
- Safety monitoring: An independent data monitoring committee (IDMC) (including paediatricians and a statistician) will be put in place to oversee the safety aspects including neurodevelopmental status of infants born to mothers vaccinated with *Boostrix* during pregnancy or immediately post-delivery in the clinical study i.e., each SAE/incidence of grade 3 local and general solicited AEs, unsolicited AEs will be reviewed by this committee *as per approved IDMC charter. (Amended 12 December 2016)*.

## 4. STUDY COHORT

### 4.1. Number of subjects/centres

A maximum of 680 infants aged 9 months will be enrolled in this study. Blood samples will be taken from all subjects in order to evaluate the immunogenicity endpoints. The tracking of recruitment of subjects into the study will be performed using SBIR.

Overview of the recruitment plan:

- Enrolment will be offered to all eligible infants born to mothers from the 116945 [DTPA (BOOSTRIX)-047] study *and having completed their primary vaccination series as per protocol requirement in study 201330 [DTPA (BOOSTRIX)-048 PRI]. (Amended 12 December 2016)*
- The study will be monitored by a local Study Monitor.
- The treatment allocation and confirmation of the enrolment of subjects into the study will be tracked using SBIR.

#### **4.2. Inclusion criteria for enrolment**

Deviations from inclusion criteria are not allowed because they can potentially jeopardise the scientific integrity of the study, regulatory acceptability or subject safety. Therefore, adherence to the criteria as specified in the protocol is essential.

All subjects must satisfy ALL the following criteria at study entry:

- Subjects' parent(s)/LAR(s) who, in the opinion of the investigator, can and will comply, with the requirements of the protocol (e.g., completion of the diary cards, return for follow-up visits).
- Written informed consent obtained from the parent(s)/LAR(s) of the subject prior to performing any study specific procedure.
- A male or female child 9 months of age at the time of enrolment.
- Healthy subjects as established by medical history and clinical examination before entering into the study.
- Subjects born to mothers who were vaccinated in 116945 [DTPA (BOOSTRIX)-047] study *and having completed their primary vaccination series as per protocol requirement in study 201330 [DTPA (BOOSTRIX)-048 PRI]. (Amended 12 December 2016)*

#### **4.3. Exclusion criteria for enrolment**

Deviations from exclusion criteria are not allowed because they can potentially jeopardise the scientific integrity of the study, regulatory acceptability or subject safety. Therefore, adherence to the criteria as specified in the protocol is essential.

The following criteria should be checked at the time of study entry. If ANY exclusion criterion applies, the subject must not be included in the study:

- Child in care  
Please refer to the [glossary of terms](#) for the definition of child in care.
- Concurrently participating in another clinical study, within three months prior to the booster vaccine dose and at any time during the present booster study, in which the subject has been or will be exposed to an investigational or a non-investigational vaccine/product (pharmaceutical product or device).

**CONFIDENTIAL**

201334 [DTPA (BOOSTRIX)-049 BST: 048]  
Protocol Amendment 1 Final

- Chronic administration (defined as more than 14 days in total) of immunosuppressants or other immune-modifying drugs during the period within six months prior to the booster vaccine dose. For corticosteroids, this will mean prednisone  $\geq 0.5\text{mg/kg/day}$ , or equivalent. Inhaled and topical steroids are allowed.
- Administration of long-acting immune-modifying drugs at any time during the study period (e.g., infliximab).
- A vaccine not foreseen by the study protocol administered during the period starting from 30 days before the booster dose of study vaccine and ending 30 days after\*, with the exception of inactivated influenza vaccine and other vaccines given as a part of the national/regional immunisation schedule, that are allowed at any time during the study period.

\*In case an emergency mass vaccination for an unforeseen public health threat (e.g.: a pandemic) is organised by the public health authorities, outside the routine immunisation program, the time period described above can be reduced if necessary for that vaccine provided it is licensed and used according to its SPC or Product Information (PI) and according to the local governmental recommendations and provided a written approval of the Sponsor is obtained.

- Any confirmed or suspected immunosuppressive or immunodeficient condition, based on medical history and physical examination (no laboratory testing required).
- Major congenital defects.
- Serious chronic illness.
- Administration of immunoglobulins and/or any blood products during the period within three months before the booster dose of study vaccines or planned administration during the study period.
- Encephalopathy defined as an acute, severe central nervous system disorder occurring within seven days following vaccination with *Infanrix hexa* and generally consisting of major alterations in consciousness, unresponsiveness, generalised or focal seizures that persist more than a few hours, with failure to recover within 24 hours.
- History of Hib, diphtheria, tetanus, pertussis, pneumococcal, poliovirus and hepatitis B diseases since the conclusion visit of study 201330 [DTPA (BOOSTRIX)-048 PRI].
- Previous booster vaccination against Hib, diphtheria, tetanus, pertussis, pneumococcus, hepatitis B and/or poliovirus since the conclusion visit of study 201330 [DTPA (BOOSTRIX)-048 PRI].
- History of any reaction or hypersensitivity likely to be exacerbated by any component of the vaccines (e.g.: antigen, excipients).
- Hypersensitivity to latex.
- History of any neurological disorders or seizures.
- Any condition that in the judgment of the investigator would make intramuscular injection unsafe.

- Acute disease and/or fever at the time of vaccination.
  - Fever is defined as temperature  $\geq 37.5^{\circ}\text{C}/99.5^{\circ}\text{F}$  for oral, axillary or tympanic route, or  $\geq 38.0^{\circ}\text{C}/100.4^{\circ}\text{F}$  on rectal route.
  - Subjects with a minor illness (such as mild diarrhoea, mild upper respiratory infection) without fever may be enrolled at the discretion of the investigator.

## 5. CONDUCT OF THE STUDY

### 5.1. Regulatory and ethical considerations, including the informed consent process

The study will be conducted in accordance with all applicable regulatory requirements.

The study will be conducted in accordance with the *International Conference on Harmonization* (ICH) Guideline for Good Clinical Practice (GCP), all applicable subject privacy requirements and the guiding principles of the Declaration of Helsinki. **(Amended 12 December 2016)**

The study has been designed and will be conducted in accordance with the ICH Harmonised Tripartite Guideline for clinical investigation of medicinal products in the paediatric population (ICH E11) and all other applicable ethical guidelines.

GSK will obtain favourable opinion/approval to conduct the study from the appropriate regulatory agency, in accordance with applicable regulatory requirements, prior to a site initiating the study in that country.

Conduct of the study includes, but is not limited to, the following:

- Institutional Review Board (IRB)/Independent Ethics Committee (IEC) review and favourable opinion/approval of study protocol and any subsequent amendments.
- Subject's parent(s)/LAR(s) informed consent, as appropriate.
- Investigator reporting requirements as stated in the protocol.

GSK will provide full details of the above procedures to the investigator, either verbally, in writing, or both.

Freely given and written or witnessed/thumb printed informed consent must be obtained from each subject's parent(s)/LAR(s), as appropriate, prior to participation in the study.

GSK Biologicals will prepare a model Informed Consent Form (ICF) which will embody the ICH GCP and GSK Biologicals required elements. While it is strongly recommended that this model ICF is to be followed as closely as possible, the informed consent requirements given in this document are not intended to pre-empt any local regulations which require additional information to be disclosed for informed consent to be legally effective. Clinical judgement, local regulations and requirements should guide the final structure and content of the local version of the ICF.

The investigator has the final responsibility for the final presentation of the ICF, respecting the mandatory requirements of local regulations. The ICF generated by the investigator with the assistance of the sponsor's representative must be acceptable to GSK Biologicals and be approved (along with the protocol, and any other necessary documentation) by the IRB/IEC.

## **5.2. Subject identification and randomisation of treatment**

### **5.2.1. Subject identification**

Subjects will retain the same subject number as their mothers in the 116945 [DTPA (BOOSTRIX)-047] study *and their own subject number in study 201330 [DTPA (BOOSTRIX)-048 PRI]*. These subject numbers will also be used to identify blood samples collected in the study. **(Amended 12 December 2016)**

### **5.2.2. Randomisation of treatment**

#### **5.2.2.1. Treatment allocation to the subject**

There will be no randomisation of subjects into groups in this study. The infants enrolled in this study will be allocated to the same groups as their mothers in the 116945 [DTPA (BOOSTRIX)-047] study *and as themselves in study 201330 [DTPA (BOOSTRIX)-048 PRI]*. Subjects will retain the same subject number as their corresponding mothers from the 116945 [DTPA (BOOSTRIX)-047] study. **(Amended 12 December 2016)**

The treatment numbers will be allocated by dose.

##### **5.2.2.1.1. Study group and treatment number allocation**

The target will be to enrol maximum of 680 eligible subjects aged 9 months (approximately 340 subjects in each group).

After obtaining the signed and dated ICF from the subject's parent(s)/LAR(s) and having checked the eligibility of the subject, *investigator or designate will complete a standardised developmental screening tool, Ages and Stages Questionnaire-3 via a paper questionnaire (at Visit 1) with* subjects' parent(s)/LAR(s). At Visit 2, the site staff in charge of the vaccine administration will access SBIR. Upon providing the subject identification number, the randomisation system will provide the treatment number to be used for *vaccination*. **(Amended 12 December 2016)**

The number of each administered treatment must be recorded in the eCRF on the Vaccine Administration screen.

When SBIR is not available, please refer to the SBIR user guide or the Study Procedures Manual (SPM) for specific instructions.

### 5.3. Method of blinding

This study will be conducted in an open-label manner since the treatment allocation is similar between the two groups. Also, the data related to the study groups will be unblinded at the end of study 116945 [DTPA (BOOSTRIX)-047].

Note: The study personnel operating SBIR and the site staff will remain blinded towards the treatment allocation *of the mother in study 116945 [DTPA (BOOSTRIX)-047]* until the completion and unblinding of study 116945 [DTPA (BOOSTRIX)-047] to prevent the potential unblinding of the treatment allocation to the mother in 116945 [DTPA (BOOSTRIX)-047]. (Amended 12 December 2016)

The laboratory in charge of the laboratory testing will be blinded to the treatment, and codes will be used to link the subject and study (without any link to the treatment attributed to the subject) to each sample.

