## CONFIDENTIAL

201334 [DTPA (BOOSTRIX)-049 BST: 048]  
Protocol Amendment 1 Final

- Control Group: This group will consist of infants born to mothers belonging to the Control group in study 116945 [DTPA (BOOSTRIX)-047], i.e., mothers who received a single dose of placebo during pregnancy and a dose of *Boostrix* immediately post-delivery and infants who **received full** primary vaccination course **as per protocol requirement** in the study 201330 [DTPA (BOOSTRIX)-048 PRI]. All infants in this group will receive a booster dose of *Infanrix hexa* co-administered with *Prevenar 13* **according to the routine national/ local immunization schedule or as specified in the SPM. (Amended 12 December 2016)**

The study will be open-label since the treatment allocation is similar between the two groups. Also, the data related to the study groups will be unblinded at the end of study 116945 [DTPA (BOOSTRIX)-047].

Currently, the effect of *Boostrix* administered to mothers during pregnancy or immediately post-delivery on the neurodevelopment of infants is unknown. Therefore, the neurodevelopment of the subjects will be studied at 9 months and 18 months of age in this study. To assess the neurodevelopmental status, the **investigator or designate** will complete a standardised developmental screening tool, Ages and Stages Questionnaire-3 (ASQ-3) via a paper questionnaire **with subjects' parent(s)/LAR(s) during the study visits or phone call** [ASQ-3, 2016]. (Amended 12 December 2016)

Any subject who scores below the cut-off i.e., a score more than 2 Standard Deviations (SDs) below the mean score for the U.S. reference group (i.e., black zone in the score chart) in any of the five domains of the ASQ-3 (i.e., communication, gross motor, fine motor, problem solving, and personal-social) will be referred to a developmental specialist for formal neurodevelopmental assessment (e.g., using the Bayley Scale for Infant Development, Version III [BSID-III]) [Bayley-III, 2006]. An overall neurodevelopmental assessment in the areas of cognitive, language, motor, social-emotional and adaptive behaviour will be rendered using BSID-III. A BSID-III score more than 2 SDs below the mean score for the U.S. reference group will be considered as a neurodevelopmental impairment.

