**CONFIDENTIAL**

201334 [DTPA (BOOSTRIX)-049 BST: 048]  
Protocol Amendment 1 Final

dose of *Infanrix hexa* co-administered with *Prevenar 13* between 11-18 months of age **according to the routine national/ local immunization schedule or as specified in the SPM. (Amended 12 December 2016)**

- Treatment allocation: Non-randomised. All subjects will receive a booster dose of *Infanrix hexa* co-administered with *Prevenar 13*.
- Blinding: Open-label.

Note: The study personnel operating SBIR and the site staff will remain blinded towards the treatment allocation **of the mother in** study 116945 [DTPA (BOOSTRIX)-047]. **(Amended 12 December 2016)**

The blinding of the study is given in Synopsis Table 3.

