**Table 2 Study groups and treatment foreseen in the study**

(Amended 12 December 2016)

Treatment name	Vaccine name	Study Groups	
		dTpa Group	Control Group
Infanrix hexa	DTPa -HBV-IPV	x	x
	Hib	x	x
Prevenar 13	Prevenar 13	x	x

- Control: uncontrolled (*No active control or placebo. All subjects will receive the same vaccine*)
- Vaccination schedule: All subjects will receive a booster dose of *Infanrix hexa* co-administered with *Prevenar 13* between **11-18** months of age *according to the routine national/ local immunization schedule or as specified in the SPM. (Amended 12 December 2016)*
- Treatment allocation: Non-randomised. All subjects will receive a booster dose of *Infanrix hexa* co-administered with *Prevenar 13*.
- Blinding: Open-label. Note: The study personnel operating with the **GSK Biologicals' central Randomisation System on Internet (SBIR)** and the site staff will remain blinded towards the treatment allocation *of the mother in* study 116945 [DTPA (BOOSTRIX)-047]. **(Amended 12 December 2016)**

The blinding of study epoch is presented in [Table 3](#).

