- Blinding: Open-label. Note: The study personnel operating with the GSK Biologicals' central Randomisation System on Internet (SBIR) and the site staff will remain blinded towards the treatment allocation of the mother in study 116945 [DTPA (BOOSTRIX)-047].

The blinding of study epoch is presented in [Table 3](#).

Table 3 Blinding of study epoch

Study Epoch	Blinding
Epoch 001	open

- Sampling schedule: Blood samples will be drawn from all subjects at the following time points:
 - Pre-Bst: Before the booster dose administration, a volume of approximately 5 mL of whole blood (to provide approximately 1.7 mL of serum) will be collected.
 - Post-Bst: One month after the booster dose, approximately 5 mL of whole blood (to provide approximately 1.7 mL of serum) will be collected.
- Type of study: extension of other protocol(s) 116945 [DTPA (BOOSTRIX)-047] and 201330 [DTPA (BOOSTRIX)-048 PRI].
- Data collection: Electronic Case Report Form (eCRF).
- Safety monitoring: An independent data monitoring committee (IDMC) (including paediatricians and a statistician) will be put in place to oversee the safety aspects including neurodevelopmental status of infants born to mothers vaccinated with *Boostrix* during pregnancy or immediately post-delivery in the clinical study i.e., each SAE/incidence of grade 3 local and general solicited AEs, unsolicited AEs will be reviewed by this committee as per approved IDMC charter.

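### Section 5.3 lets the site-staff blind to the mother's allocation lapse when study 116945 is unblinded, and nothing masks the BSID-III specialist, so some 18-month neurodevelopment assessments may be unmasked

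*Protocol*

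**What the plan says.** Four places carry a blinding note for site staff. Protocol Section 3 says that SBIR personnel "and the site staff will remain blinded towards the treatment allocation *of the mother in* study 116945 [DTPA (BOOSTRIX)-047"; the synopsis has the same note, and SAP Section 2 repeats that "the site staff will remain blinded towards the treatment allocation of the mother in study 116945 [DTPA (BOOSTRIX)-047". None of these three says when the blind stops. Protocol Section 5.3 does: it holds "until the completion and unblinding of study 116945 [DTPA (BOOSTRIX)-047] to prevent the potential unblinding" of the mother's allocation.

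The synopsis rationale, Section 1.2.2 and Section 5.3 add a separate statement: "Also, the data related to the study groups will be unblinded at the end of study 116945 [DTPA (BOOSTRIX)-047". The reason given for running the study open-label is this: "This study will be conducted in an open-label manner since the treatment allocation is similar between the two groups". Section 5.2.2.1 keeps each infant in the mother's group, and "Subjects will retain the same subject number as their corresponding mothers from the 116945 [DTPA (BOOSTRIX)-047] study".

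Section 1.2.2 states that the effect on infant neurodevelopment of giving Boostrix in pregnancy or just after delivery is not known. Under Section 5.6.2.13 the investigator or a designee completes the ASQ-3 with the parent, at a visit or by phone. A black-zone score in any domain leads to referral to a developmental specialist, whose overall judgement goes into the eCRF.

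**The concern.** The open-label rationale concerns what the infants receive, which is the same in both groups. The neurodevelopment question concerns what the mother received and when, so maternal allocation is the exposure for that endpoint and the rationale does not cover it. The only protection for the interviewers is a note written to safeguard 116945, and it stops when 116945 no longer needs it. The specialist was never covered by the note.

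Both assessments involve judgement: how a question is put and scored in an interview, and how a specialist rates a child. Someone who knows the maternal group could be influenced, and such an influence cannot be removed after the data are collected. What is at stake is how readers interpret the by-group ASQ-3 and BSID-III percentages, the endpoint meant to address an effect that the protocol calls unknown.

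**Working it through.** The plan gives no figure on this point, so the main check is a comparison of texts, followed by a question of timing.

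**Masking statements side by side**

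| Place | Who | End of the blind |
|---|---|---|
| Protocol synopsis, blinding note | SBIR personnel, site staff | none given |
| Protocol Section 3, blinding note | SBIR personnel, site staff | none given |
| SAP Section 2, blinding note | SBIR personnel, site staff | none given |
| Protocol Section 5.3 | SBIR personnel, site staff | completion and unblinding of 116945 |
| Protocol Section 5.3 | testing laboratory: "The laboratory in charge of the laboratory testing will be blinded to the treatment" | none given |
| Protocol Section 5.4.4 | safety review team (reviews blinded data) | none given |
| Protocol 5.6.2.13, Table 4 and Table 13 footnotes; SAP 5.4, 9.1.2, 9.2 and Templates 29–31 | BSID-III specialist | no masking stated |

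The first three rows are silent on the end point; they do not state a different one. Read with Section 5.3, the rule is: blind until 116945 is unblinded.

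**Is there a check in the SAP?** Elimination code 1060 (randomisation code broken) applies to the ATP cohorts for safety and immunogenicity (SAP 4.2.2.1). Templates 29–31 use the Total enrolled cohort, so that code does not act on the neurodevelopment tables.

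**Can an 18-month ASQ-3 fall after unblinding?** Inputs:
- Infant follow-up in 116945: two months after birth (SAP 9.1.1).
- Second ASQ-3 at A = 18 months; the window is 17 months 0 days to 18 months 30 days (Protocol Table 5 footnote).
- L, months from the last-born infant leaving 116945 to its unblinding: not given. As a guide only, this protocol's glossary allows up to 8 months from last visit to end of study; 116945 may differ.
- R, length of the 116945 birth period in months: not given.

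At unblinding the last-born infant is 2 + L months old. That infant's 18-month ASQ-3 comes later if 18 > 2 + L, that is, if L < 16. If births are spread evenly over R months, the share of infants assessed after unblinding is (A − 2 − L)/R, limited to 0–100%. For A = 18 and assumed values:

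| L | R = 12 | R = 24 | R = 36 |
|---|---|---|---|
| 3 | 13/12, so 100% | 13/24 = 54% | 13/36 = 36% |
| 8 | 8/12 = 67% | 8/24 = 33% | 8/36 = 22% |
| 12 | 4/12 = 33% | 4/24 = 17% | 4/36 = 11% |

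For the 9-month ASQ-3 the share is 0% once L reaches 7 (9 − 2 − 7 = 0).

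The range of 11% to 100% is too wide to be an estimate, and it counts assessments done after unblinding, not assessments by people who know the allocation. It shows only that some 18-month assessments can fall after the blind ends.

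**The case against.** The strongest reply is that nothing here is hidden or contradictory. The study is declared open-label throughout, and the glossary says that an open-label study uses no blind. Section 5.3 is the full rule, the other three notes are summaries, and the rule's stated purpose was to protect 116945. Harm needs a chain: 116945 unblinded before some 18-month assessments, individual codes sent to sites, the assessor knowing them, and that knowledge changing a rating. No link is documented. The Study Procedures Manual, which is not among the documents, may contain masking instructions. The black-zone cut-offs are fixed (SAP 9.1.2), referral follows a rule, and all analyses are descriptive.

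Much of this stands, and it rules out several stronger readings:
- A reader might infer that the blinding notes conflict. They do not; three omit a detail that the fourth supplies.
- A reader might infer that sites will be unblinded, since group data are opened at the end of 116945. The documents do not say that individual codes go to sites. The shared subject number means only that a released code would identify the infant's group without a further linking step.
- A reader might subtract 2 from 17 and from 19 months and conclude that every 18-month ASQ-3 falls 15 to 17 months after follow-up in 116945. That gap runs from the infant's own exit, not from unblinding of the whole study, and it fails for infants born three or more weeks early, whose age is corrected for prematurity.
- A reader might infer that the specialist knows the group. Lack of masking does not show knowledge.

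What the reply does not answer is that the open-label rationale leaves maternal exposure uncovered, and that both documents are silent on masking the specialist.

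**Conclusion.** The point holds as a gap in masking, not as a demonstrated bias. Section 5.3 lets the site-staff blind lapse when 116945 is unblinded, three other notes omit that limit, and the BSID-III specialist is masked nowhere in either document. Some 18-month ASQ-3 interviews and resulting BSID-III assessments may therefore be done by assessors who could know the exposure under study. Neither the share affected nor any bias can be determined from the documents.

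This rests on two assumptions: that 116945 is unblinded less than 16 months after its last-born infant leaves, and that no masking rule exists in documents not seen. The consequence is limited to a secondary, descriptive endpoint and excludes the fixed cut-offs, the rule-based referral and the laboratory-based primary endpoint. The change is worth making because it is cheap and the outcome depends on judgement. Confidence is medium.

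**What to change.** 1. Amend Protocol Section 5.3, and align the notes in the synopsis, Section 3 and SAP Section 2, to one rule. Site staff who conduct the ASQ-3 and specialists who perform the BSID-III are not given the mother's individual 116945 allocation until that infant's 18-month ASQ-3 and any resulting BSID-III are recorded. Keep an exception where a serious adverse event requires unblinding, as the glossary already foresees.
2. In the synopsis rationale, Section 1.2.2 and Section 5.3, clarify only that the unblinding at the end of 116945 concerns group-level data and does not release individual codes to these assessors. Group-level reporting of 116945 can go ahead.
3. The parent is the main informant for the ASQ-3. Where the 116945 arrangements allow, ask sites not to tell parents the individual allocation before the 18-month ASQ-3; otherwise state this as a limitation.
4. If codes have already been released, report by group, alongside Templates 29–31, the number of ASQ-3 and BSID-III assessments done after release, and state the limitation in the study report. A before/after split of the results is not advised: it would be confounded with calendar time and possibly with country and primary schedule, since two-dose countries were added by amendment.

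Cost: wording changes and no extra staff. Sites, and possibly parents, learn individual allocation later. Timing must be coordinated with the 116945 protocol and consent, which are not among these documents. The count in step 4 needs release dates by site.
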